**Table 25.2-1: Definitions**

Term	Definition						
	
 
○ Anasarca
 
○ Presence of “hepato-jugular reflux”
 
○ Edema
 
 Severe right ventricular dysfunction or severe pulmonary hypertension is primary or secondary pulmonary hypertension with PA systolic pressures greater than 2/3 of systemic pressure.						
SERIOUS ADVERSE EVENT (SAE) Ref: ISO 14155 Ref: MEDDEV 2.7/3	
Note 1: This definition meets the reporting objectives and requirements of ISO 14155 and MEDDEV 2.7/3.
 
Adverse event that:
 
 
• Led to death,
 
• Led to serious deterioration in the health of the subject as defined by either:                             
 
○ a life-threatening illness or injury, or
 
○ a permanent impairment of a body structure or a body function, or
 
○ in-patient hospitalization or prolongation of existing hospitalization, or
 
○ medical or surgical intervention to prevent life-threatening illness or injury or permanent impairment to a body structure or a body function
 
 
 
• Led to fetal distress, fetal death, or a congenital abnormality or birth defect.
 
 
Note 2: Planned hospitalization for a pre-existing condition, or a procedure required by the clinical investigational plan, without a serious deterioration in health, is not considered a serious adverse event.
						
SERIOUS ADVERSE DEVICE EFFECT (SADE) Ref: ISO 14155 Ref: MEDDEV 2.7/3	Adverse device effect that has resulted in any of the consequences characteristic of a serious adverse event						
SOURCE DATA (per ISO 14155:2011)	All information in original records of clinical findings, observations, or other activities in a clinical investigation, necessary for the reconstruction and evaluation of the clinical investigation						
SOURCE DOCUMENT (per ISO 14155:2011)	Printed, optical or electronic document containing source data. Examples: Hospital records, laboratory notes, device accountability records, photographic negatives, radiographs, records kept at the investigation center, at the laboratories and at the medico-technical departments involved in the clinical investigation.						
STROKE NeuroARC   Neurological Event Definitions	
  
 Type	Description	
   
 Type 1 – Overt CNS Injury: Acutely Symptomatic Brain or Spinal Cord Injury	
 
 Type 1.a Ischemic stroke	                             Sudden onset of neurological signs or symptoms fitting a focal or multifocal vascular territory within the brain, spinal cord, or retina, that:                             
 
1. Persist for ≥24 h or until death, with pathology or neuroimaging evidence that demonstrates either:                                     
 
a. CNS infarction in the corresponding vascular territory (with or without hemorrhage); or
 
b. Absence of other apparent causes (including hemorrhage), even if no evidence of acute ischemia in the corresponding vascular territory is detected
 
 
 
                             or                         	
  
	Type	Description	Type 1 – Overt CNS Injury: Acutely Symptomatic Brain or Spinal Cord Injury		Type 1.a Ischemic stroke	Sudden onset of neurological signs or symptoms fitting a focal or multifocal vascular territory within the brain, spinal cord, or retina, that: 
 
1. Persist for ≥24 h or until death, with pathology or neuroimaging evidence that demonstrates either:                                     
 
a. CNS infarction in the corresponding vascular territory (with or without hemorrhage); or
 
b. Absence of other apparent causes (including hemorrhage), even if no evidence of acute ischemia in the corresponding vascular territory is detected
 
 
 
 or
	Type	Description					
	Type 1 – Overt CNS Injury: Acutely Symptomatic Brain or Spinal Cord Injury						
Type 1.a Ischemic stroke	Sudden onset of neurological signs or symptoms fitting a focal or multifocal vascular territory within the brain, spinal cord, or retina, that: 
 
1. Persist for ≥24 h or until death, with pathology or neuroimaging evidence that demonstrates either:                                     
 
a. CNS infarction in the corresponding vascular territory (with or without hemorrhage); or
 
b. Absence of other apparent causes (including hemorrhage), even if no evidence of acute ischemia in the corresponding vascular territory is detected
 
 
 
 or						

**Table 25.2-1: Definitions**

Term	Definition
	
2. Symptoms lasting <24 h, with pathology or neuroimaging confirmation of CNS infarction in the corresponding vascular territory. Note: When CNS infarction location does not match the transient symptoms, the event would be classified as covert CNS infarction (Type 2a) and a TIA (Type 3a), but not as an ischemic stroke.
 
Signs and symptoms consistent with stroke typically include an acute onset of 1 of the following: focal weakness and/or numbness; impaired language production or comprehension; homonymous hemianopia or quadrantanopsia; diplopia; altitudinal monocular blindness; hemispatial neglect; dysarthria; vertigo; or ataxia.

Type 2 – Covert CNS Injury: Acutely Asymptomatic Brain or Spinal Cord Injury Detected by Neuroimaging
	

Type 2.a Covert CNS infarction
	
Brain, spinal cord, or retinal cell death attributable to focal or multifocal ischemia, on the basis of neuroimaging or pathological evidence of CNS infarction, without a history of acute neurological symptoms consistent with the lesion location

Subtype 2.a.H Covert CNS infarction with hemorrhagic conversion
	
Covert CNS infarction includes hemorrhagic conversions. These should be subclassified as Class A or B when CNS infarction is the primary mechanism and neuroimaging or pathology confirms a hemorrhagic conversion.
 
Class A: Petechial hemorrhage: Petechiae or confluent petechiae within the infarction or its margins, but without a space-occupying effect
 
Class B: Confluent hemorrhage: Confluent hemorrhage originating from within the infarcted area with a space-occupying effect

Type 2.b Covert CNS hemorrhage
	
Neuroimaging or pathological evidence of CNS hemorrhage within the brain parenchyma, subarachnoid space, ventricular system, spinal cord, or retina on neuroimaging that is not caused by trauma, without a history of acute neurological symptoms consistent with the bleeding location.

Type 3 – Neurological Dysfunction (Acutely Symptomatic) Without CNS Injury
	

Type 3.a Transient ischemic attack
	
Transient focal neurological signs or symptoms (lasting <24 h) presumed to be due to focal brain, spinal cord, or retinal ischemia, but without evidence of acute infarction by neuroimaging or pathology (or in the absence of imaging).


Type 3.b Delirium without CNS injury
	
Transient nonfocal (global) neurological signs or symptoms (variable duration) without evidence of cell death by neuroimaging or pathology.

Composite Neurological Endpointsa
	

CNS infarction
	
Any brain, spinal cord, or retinal infarction on the basis of imaging, pathology, or clinical symptoms persisting for ≥24 h (includes Types 1.a, 1.a.H, 1.d, 1.e, 2.a, 2.a.H)

CNS hemorrhage
	
Any brain, spinal cord, or retinal hemorrhage on the basis of imaging or pathology, not caused by trauma (includes Type 1.b,

**Table 25.2-1: Definitions**

Term	Definition
	
1.c, 2.b)
 
a: Neurological endpoints are not mutually exclusive; an individual subject may have >1 event. VARC-defined stroke includes all Type 1 events (stroke and symptomatic hypoxic-ischemic injury). American Stroke Association-defined stroke includes Type 1.a–d events (overt [focal only] CNS injury), and Type 2.a and 2.a.H (covert CNS infarction).


STROKE                      VARC
	
Stroke is defined as an acute episode of focal or global neurological dysfunction caused by brain, spinal cord, or retinal vascular injury as a result of hemorrhage or infarction
 
Stroke Classification
 
 
• Ischemic Stroke is defined as an acute episode of focal cerebral, spinal, or retinal dysfunction caused by an infarction of central nervous system tissue.
 
• Hemorrhagic Stroke is defined as an acute episode of focal or global cerebral or spinal dysfunction caused by an intraparenchymal, intraventricular, or subarachnoid hemorrhage
 
 
Note 1: The CEC will adjudicate ischemic versus hemorrhagic stroke.  Note 2: A stroke may be classified as undetermined if there is insufficient information to allow categorization as ischemic or hemorrhagic
 
Stroke Diagnostic Criteria
 
 
• Rapid onset of a focal or global neurological deficit with at least one of the following: change in level of consciousness, hemiplegia, hemiparesis, numbness or sensory loss affecting one side of the body, dysphasia or aphasia, hemianopia, amaurosis fugax, or other neurological signs or symptoms consistent with stroke
 
• Duration of a focal or global neurological deficit <math>\geq 24</math> h; OR <math>< 24</math> h, if available neuroimaging documents a new hemorrhage or infarct; OR the neurological deficit results in death
 
• No other readily identifiable nonstroke cause for the clinical presentation (e.g., brain tumor, trauma, infection, hypoglycemia, peripheral lesion, pharmacological influences), to be determined by or in conjunction with designated neurologist
 
• Confirmation of the diagnosis by at least one of the following.                         
 
○ Neurology or neurosurgical specialist
 
○ Neuroimaging procedure (MRI or CT scan), but stroke may be diagnosed on clinical grounds alone
 
 
 
 
Note 3: Subjects with non-focal global encephalopathy will not be reported as a stroke without unequivocal evidence based upon neuroimaging studies (CT scan or brain MRI).
 
Stroke Definitions
 
Diagnosis as above, preferably with positive neuroimaging study
 
 
• Non-disabling: Modified Rankin Scale (mRS) score <math>< 2</math> at 90 days OR one that does not result in an increase of at least one mRS category from an individual’s pre-stroke baseline
 
• Disabling: Modified Rankin Scale score <math>\geq 2</math> at 90 days AND an increase of at least one mRS category from an individual’s pre-stroke baseline
 
 
Note 4: Modified Rankin Scale assessments should be made by qualified individuals according to a certification process.


Table 25.2-1: Definitions

Term	Definition
	Note 5: Assessment of the mRS score should occur at baseline; mRS also should be performed after a stroke and at 90 days after the onset of any stroke.
STRUCTURAL VALVE DETERIORATION (SVD)	Component of time-related valve safety defined as follows. 
 
Valve-related dysfunction: Mean aortic valve gradient <math>\geq 20</math> mmHg, EOA <math>\leq 0.9</math>-<math>1.1</math> cm^2, and/or DVI <math>< 0.35</math> AND/OR moderate or severe prosthetic valve regurgitation (per VARC definition)
 
Requiring repeat procedure (TAVR or SAVR).
 
 Note: Additional outcomes may be measured per definitions set in the most current VARC guidelines (as released at the time of analysis).
SURGICAL RISK 	Surgical risk is determined by the Heart Team, including a center cardiac surgeon. 
Note: Input from the Heart Team regarding anatomic or functional factors not reflected in the Society of Thoracic Surgeons predicted risk of mortality (STS-PROM) score may increase patient risk above the definitions provided below.
 
Extreme Risk: Predicted operative mortality risk <math>\geq 15\%</math> at 30 days as determined by STS-PROM score
 
High Risk: Predicted operative mortality risk <math>\geq 8\%</math> at 30 days as determined by STS-PROM score
 
Intermediate Risk: Predicted operative mortality risk <math>\geq 3\%</math> and <math>< 8\%</math> at 30 days as determined by STS-PROM score
 
Low Risk: Predicted operative mortality risk <math>< 3\%</math> at 30 days as determined by STS-PROM score

TAV-IN-TAV DEPLOYMENT	An additional valve prosthesis is implanted within a previously implanted prosthesis because of suboptimal device position and/or function during or after the index procedure.
TRANSIENT ISCHEMIC ATTACK (TIA)	
 
Transient episode of focal neurological dysfunction caused by brain, spinal cord, or retinal ischemia, without acute infarction
 
Duration of a focal or global neurological deficit is <math>< 24</math> h
 
Neuroimaging does not demonstrate a new hemorrhage or infarct (if performed)
 
 Note: The difference between TIA and ischemic stroke is the presence of tissue damage or new sensory-motor deficit persisting $> 24$ hours. By definition, TIA does not produce lasting disability.
UNANTICIPATED ADVERSE DEVICE EFFECT (UADE)  Ref: 21 CFR Part 812	Any serious adverse effect on health or safety or any life-threatening problem or death caused by, or associated with, a device, if that effect, problem, or death was not previously identified in nature, severity, or degree of incidence in the investigational plan or application (including a supplementary plan or application), or any other unanticipated serious problem associated with a device that relates to the rights, safety, or welfare of subjects.
UNANTICIPATED SERIOUS ADVERSE DEVICE EFFECT (USADE)  Ref: ISO 14155 Ref: MEDDEV 2.7/3	Serious adverse device effect which by its nature, incidence, severity, or outcome has not been identified in the current version of the risk analysis report Note: An anticipated serious adverse device effect (ASADE) is an effect which by its nature, incidence, severity, or outcome has been identified in the risk analysis report.
UNPLANNED USE OF CPB	Unplanned use of cardiopulmonary bypass (CPB) for hemodynamic support at any time during the TAVR procedure

**Table 25.2-1: Definitions**

Term	Definition
VALVE EMBOLIZATION	The valve prosthesis moves during or after deployment such that it loses contact with the aortic annulus.
VALVE MALAPPOSITION	Includes valve migration, valve embolization, ectopic valve deployment, or transcatheter aortic valve (TAV)-in-TAV deployment.
VALVE MIGRATION	After initial correct positioning the valve prosthesis moves upward or downward within the aortic annulus from its initial position, with or without consequences (e.g., regurgitation).
VALVE-RELATED DYSFUNCTION	Mean aortic valve gradient $\geq 20$ mmHg, EOA $\leq 0.9$ - $1.1$ cm  , and/or DVI $< 0.35$ AND/OR moderate or severe prosthetic valve aortic regurgitation (per VARC definition)
VALVE THROMBOSIS	Any thrombus attached to or near an implanted valve that occludes part of the blood flow path, interferes with valve function, or is sufficiently large to warrant treatment. Note that valve-associated thrombus identified at autopsy in a patient whose cause of death was not valve-related or at operation for an unrelated indication should not be reported as valve thrombosis.

**Table 25.2-1: Definitions**

Term	Definition

VASCULAR ACCESS SITE AND ACCESS RELATED COMPLICATIONS
	
Major Vascular Complications
 
 
• Any aortic dissection, aortic rupture, annulus rupture, left ventricle perforation, or new apical aneurysm/pseudoaneurysm
 
• Access site or access-related vascular injury (dissection, stenosis, perforation, rupture, arterio-venous fistula, pseudoaneurysm, hematoma, irreversible nerve injury, compartment syndrome, percutaneous closure device failure*) leading to death, life-threatening or major bleeding**, visceral ischaemia, or neurological impairment
 
• Distal embolization (non-cerebral) from a vascular source requiring surgery or resulting in amputation or irreversible end-organ damage
 
• The use of unplanned endovascular or surgical intervention associated with death, major bleeding, visceral ischaemia or neurological impairment
 
• Any new ipsilateral lower extremity ischemia documented by patient symptoms, physical exam, and/or decreased or absent blood flow on lower extremity angiogram
 
• Surgery for access site-related nerve injury
 
• Permanent access site-related nerve injury
 
 
Minor Vascular Complications
 
 
• Access site or access-related vascular injury (dissection, stenosis, perforation, rupture, arterio-venous fistula, pseudoaneurysms, hematomas, percutaneous closure device failure*) not leading to death, life-threatening or major bleeding**, visceral ischaemia or neurological impairment
 
• Distal embolization treated with embolectomy and/or thrombectomy and not resulting in amputation or irreversible end-organ damage
 
• Any unplanned endovascular stenting or unplanned surgical intervention not meeting the criteria for a major vascular complication
 
• Vascular repair or the need for vascular repair (via surgery, ultrasound-guided compression, transcatheter embolization, or stent-graft)
 
 
*Percutaneous Closure Device Failure                      Failure of a closure device to achieve hemostasis at the arteriotomy site leading to alternative treatment (other than manual compression or adjunctive endovascular ballooning)
 
Note 1: Pre-planned surgical access or a planned endovascular approach to vascular closure (e.g., “pre-closure”) should be considered as part of the TAVR procedure and not as a complication, unless untoward clinical consequences are documented (e.g., bleeding complications, limb ischemia, distal embolization, or neurological impairment).
 
Note 2: If unplanned percutaneous or surgical intervention does not lead to adverse outcomes this is not considered a major vascular complication.
 
** Refers to VARC bleeding definitions


VENTRICULAR SEPTAL PERFORATION
	
Angiographic or echocardiographic evidence of a new septal perforation during or after the TAVR procedure

VESSEL PERFORATION
	
Unexpected puncture of the vessel with evidence of extravasation into extraluminal surrounding tissue or space requiring treatment using interventional or surgical techniques

Abbreviations: ADE=adverse device effect; AE=adverse event; AR=aortic regurgitation; AVA=aortic valve area; AVR= aortic valve replacement; CEC=Clinical Events Committee; CK=creatinine kinase; CNS=central

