#### 5.1. Overview of the Sentinel® Cerebral Protection System

[figure not shown]
The commercially available Sentinel Cerebral Protection System (Sentinel; Boston Scientific Corporation, Marlborough, MA, USA) is designed to capture and remove debris dislodged during endovascular procedures. It consists of 2 filters within a single 6-F delivery catheter percutaneously placed from the right radial or brachial artery over a 0.014-inch guidewire.

The major features of the system are shown in **Figure 5.1-1**. The articulating sheath tip, proximal sheath tip, proximal filter hoop, proximal articulating sheath marker, distal filter hoop and distal filter tip are radiopaque to enable visualization during use. The filters are positioned in the brachiocephalic artery (proximal filter) and the left common carotid artery (distal filter) before the TAVR procedure (**Figure 5.1-2**) and are withdrawn into the catheter and removed after TAVR. Additional product information can be found in the commercial Instructions For Use (IFU).

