#### 6.2.2. **Additional Measurements**

The additional measurements shown below are based on NeuroARC and Valve Academic Research Consortium (VARC) endpoints and definitions and will be assessed through 72 hours post TAVR procedure or discharge (whichever comes first). Mortality (cardiovascular and non-cardiovascular), neurological endpoints (stroke, transient ischemic attack [TIA], and delirium), acute kidney injury, and Sentinel access site major vascular complications will be adjudicated by an independent CEC.

- All-cause death (cardiovascular and non-cardiovascular)
- Neurological endpoints (see **Note 1** below)
  - Stroke (disabling and non-disabling)
  - Transient ischemic attack

- Delirium
- Safety composite of all-cause mortality and all stroke
- Neurological status as determined by the following (see **Note 1** below):
  - Neurological physical examination
  - Modified Rankin Scale (mRS) score
  - National Institutes of Health Stroke Scale (NIHSS)
  - Confusion Assessment Method for Intensive Care Unit Patients (CAM-ICU)
  - Montreal Cognitive Assessment (MoCA)
- Acute kidney injury based on the AKIN System^26 Stage 3 (including renal replacement therapy) and Stage 2
- Sentinel access site vascular complications related to the procedure (major and minor)
- Sentinel system acute delivery and retrieval (categorized as successful deployment of both filters, 1 filter, or no filter and retrieval of the system)
- Health status as evaluated by EQ-5D Quality of Life questionnaire at baseline

**Note 1:** The neurological physical examination must be carried out by a neurology professional (board certified/board eligible neurologist, neurology fellow, neurology physician assistant, or neurology nurse practitioner). The NIHSS, mRS, and MoCA must be performed by certified personnel. The CAM-ICU must be done by personnel with appropriate training as documented by the sponsor. In all subjects where stroke is suspected, a formal neurology/stroke consult should be obtained, and the subject should be further assessed and treated per standard of care. In subjects diagnosed with post-procedural stroke, mRS must also be administered 30±7 days following the stroke; the simplified mRS questionnaire may be used for this follow-up assessment.

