**Table 8.2-1: PROTECTED TAVR Exclusion Criteria**

- |   |
|---|
| 
EC1. Subject has arterial stenosis >70% in either the left common carotid artery or the brachiocephalic artery.
 
EC2. Subject's brachiocephalic or left carotid artery reveals significant stenosis, ectasia, dissection, or aneurysm at the aortic ostium or within 3 cm of the aortic ostium.
 
EC3. Subject has compromised blood flow to the right upper extremity.
 
EC4. Subject has access vessels with excessive tortuosity.
 
EC5. Subject has uncorrected bleeding disorders.
 
EC6. Subject is contraindicated for anticoagulant and antiplatelet therapy.
 |
|---|

**Note:** Use of general anesthesia during TAVR may affect neurocognitive function shortly after the

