## 9. Subject Accountability

### 9.1. Point of Enrollment

A subject who provides an ICF signed by the subject or the subject's legally authorized representative is considered enrolled in the study upon randomization, which will occur at the index procedure prior to procedural puncture/incision.

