## 19. Safety Reporting

### 19.1. Reportable Events by Investigational Center to Boston Scientific

It is the responsibility of the investigator to assess and report to BSC any event that occurs in any of following categories:

- All serious adverse events (SAE)
- All device-related adverse events
- All device deficiencies
- Unanticipated adverse device effects (UADE)/unanticipated serious adverse device effects (USADE)
- All CEC events (see below)
- New findings/updates in relation to already reported events

When possible, the medical diagnosis should be reported as the Event Term instead of individual symptoms.

If it is unclear whether or not an event fits one of the above categories, or if the event cannot be isolated from the device or procedure, it should be submitted as an adverse event (AE) and/or device deficiency.

Any AE required by the protocol, experienced by the study subject after informed consent and once considered enrolled in the study, whether during or subsequent to the procedure, must be recorded in the eCRF. Collection of safety events includes all CEC events (see below), regardless of seriousness and device relationship.

Underlying diseases are not reported as AEs unless there is an increase in severity or frequency during the course of the investigation. Death should not be recorded as an AE but should only be reflected as an outcome of one (1) specific SAE (see **Table 19.2-1** for AE definitions).

Refer to the Instructions For Use for the known risks associated with the commercial device.

The endpoints (see endpoint definitions in **Table 25.2-1**) requiring adjudication by the CEC include the following.

- Death: cardiovascular and non-cardiovascular
- Stroke: disabling and non-disabling
- Transient ischemic attack
- Delirium
- Acute kidney injury (Stage 2 and Stage 3)
- Sentinel access site major vascular complications related to the procedure

Details on the CEC events and procedures are outlined in the CEC charter. Tests and images required to adjudicate these events are specified in the event definitions (see **Table 25.2-1**).

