	
20,000 people and/or the initial three digits of a ZIP code for all such geographic units containing 20,000 or fewer people is changed to 000
 
 
• All elements of dates (except year) for dates that are directly related to an individual, including birth date, admission date, discharge date, death date, and all ages over 89 and all elements of dates (including year) indicative of such age, except that such ages and elements may be aggregated into a single category of age 90 or older
 
• Telephone numbers
 
• Fax numbers
 
• Device identifiers and serial numbers
 
• E-mail addresses
 
• Web Universal Resource Locators (URLs)
 
• Internet Protocol (IP) addresses
 
• Medical record numbers
 
• Biometric identifiers, including finger and voice prints
 
• Health plan beneficiary numbers
 
• Full-face photographs and any comparable images
 
• Any other unique identifying number, characteristic, or code (including subject ID number)
 

DEATH	
All-cause Death Death from any cause after a valve intervention.
 
Cardiovascular Death Any one of the following criteria is met.
 
 
• Any death due to proximate cardiac cause (e.g., myocardial infarction, cardiac tamponade, worsening heart failure)
 
• Sudden or unwitnessed death
 
• Death of unknown cause
 
• Death caused by noncoronary vascular conditions such as neurological events, pulmonary embolism, ruptured aortic aneurysm, dissecting aneurysm, or other vascular disease
 
• All procedure-related deaths, including those related to a complication of the procedure or treatment for a complication of the procedure
 
• All valve-related deaths including structural or nonstructural valve dysfunction or other valve-related adverse events
 
 
Non-cardiovascular Death
 
 
• Any death in which the primary cause of death is clearly related to another condition (e.g. trauma, cancer, suicide)
 

DELIRIUM	
Per NeuroARC, while multifactorial, delirium (global neurological dysfunction) without central nervous system injury should be adjudicated and reported due to its prognostic implications. Assessment tools include the Confusion Assessment Method for ICU Patients (CAM-ICU).

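### The major vascular complication definition has no arm-ischemia criterion, although the trial's vascular safety measure is at the Sentinel arm access site

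*Combined protocol and SAP*

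**What the plan says.** **Access route and measure.** Section 5.1 describes the device as "percutaneously placed from the right radial or brachial artery". Section 6.2.2 lists vascular complications, major and minor, only for the Sentinel access site, and states that "Sentinel access site major vascular complications will be adjudicated by an independent CEC". Minor ones are counted but not sent to the CEC. Section 19.1 repeats that only major Sentinel access-site complications are adjudicated, and adds that "Tests and images required to adjudicate these events are specified in the event definitions", pointing to Table 25.2-1.

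**Definition.** In Table 25.2-1, under vascular access site and access-related complications, the only stand-alone limb-ischemia criterion for a major complication is "Any new ipsilateral lower extremity ischemia documented by patient symptoms, physical exam, and/or decreased or absent blood flow on lower extremity angiogram". An access injury otherwise becomes major through neurological impairment, visceral ischemia, major or life-threatening bleeding, or death. Limb ischemia is not among those consequences. Exclusion criterion EC3 shows that the plan has right-arm circulation in view: "Subject has compromised blood flow to the right upper extremity".

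**Death.** Table 25.2-1 defines all-cause death as "Death from any cause after a valve intervention". The cardiovascular and non-cardiovascular lines of the same entry carry no such limit. Under Section 9.1 a consented subject is "considered enrolled in the study upon randomization, which will occur at the index procedure prior to procedural puncture/incision", and Section 11.2.1 keeps every randomized subject in the intention-to-treat (ITT) set, treated or not.

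**The concern.** The limb-ischemia criterion is written for a leg, while the access site that this trial measures is in the arm. New leg ischemia shown by symptoms alone would be major. The same finding in the arm used for Sentinel would not be, and would not reach the CEC as a vascular complication. The plan treats impaired right-arm flow as a reason not to enroll a subject, so arm ischemia is a foreseeable harm of this access route.

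The secondary issue has the same origin: a definition written around the valve rather than around this trial's starting point. Read literally, a death after randomization but before any valve intervention is outside all-cause death, and so outside the composite of death and stroke.

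At stake is whether the safety lines for the device, which Table 6.3-1 says are meant to confirm its safety, count what a reader will assume they count.

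**Working it through.** There is no plan figure to reproduce. The check is to apply the definitions to a test case and then to size one event.

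**Step 1: test case.** A subject has new ischemia of the right arm after Sentinel access, documented by symptoms and examination, with no bleeding, neurological deficit, intervention or nerve injury. Against the major criteria of Table 25.2-1:

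- Aortic, annular or ventricular injury: not met.
- Access injury with a listed consequence: not met, since limb ischemia is not a listed consequence.
- Non-cerebral distal embolization: met only if it needs surgery or ends in amputation or irreversible organ damage.
- Unplanned intervention with a listed consequence: not met.
- Limb ischemia: not met, since the criterion names the lower extremity and a lower-extremity angiogram.
- Surgery for nerve injury, or permanent nerve injury: not met.

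The case is not major.

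**Step 2: is it minor?** It is minor if a named injury such as dissection or stenosis is found, or if embolectomy, stenting, surgery or vascular repair follows or repair is needed. Vessel occlusion is defined elsewhere in the table but is not among the named access injuries. Ischemia from an occlusion that is neither repaired nor judged to need repair fits neither class.

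**Step 3: adjudication.** Sections 6.2.2 and 19.1 send only major Sentinel access-site complications to the CEC. The case in Steps 1 and 2 is not adjudicated under that heading.

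**Step 4: death.** Four pieces of text need to fit together.

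- Section 5.1: "The filters are positioned in the brachiocephalic artery (proximal filter) and the left common carotid artery (distal filter) before the TAVR procedure". A death during filter placement therefore comes before TAVR.
- Cardiovascular line of Table 25.2-1: it includes every procedure-related death, with no timing limit. The filter-placement death counts here.
- All-cause line: it starts at a valve intervention, a term the table does not define. Read literally, the same death does not count here.
- Section 11.2.1: the Per-Protocol set is restricted to subjects who have TAVR, so the plan foresees randomized subjects who do not. They remain in ITT, yet if a subject has no valve intervention at all, that subject's death is never after one.

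A death could thus fall in a cause-specific class and not in the all-cause total, although Section 6.2.2 presents all-cause death as made up of the two classes.

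**Step 5: size of one event.** Inputs from Section 11.1.1.2: 1,500 subjects per arm, a maximum of 6,000 in total (3,000 per arm at 1:1), and a planned Test stroke rate of 2%. The denominator is assumed to be the full arm.

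- One event changing class, or one death restored: 1/1500 = 0.067 percentage points; 1/3000 = 0.033 percentage points.
- Planned Test strokes: 0.02 × 1500 = 30. One omitted death without stroke, added to these, is 1 of 31 (3.2%) of the composite count. At 3,000 per arm, 0.02 × 3000 = 60, so 1 of 61 (1.6%). These shares are upper limits at the planned rate, since other deaths would enlarge the count.

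The documents give no rate for arm ischemia or for deaths before the valve intervention, so the expected number of affected events cannot be calculated. It may be zero.

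**The case against.** The strongest defense is that the definition is deliberately standard. Section 6.2.2 says the measurements follow NeuroARC and Valve Academic Research Consortium (VARC) definitions, and unmodified wording keeps the rate comparable with other trials. The other criteria already catch the graver arm events: injury with major bleeding or neurological impairment, embolization needing surgery, and permanent nerve injury. Section 19.1 leaves CEC details to a charter that was not supplied and may cover arm access. On death, the unrestricted cardiovascular and non-cardiovascular lines, which are also the two classes the CEC adjudicates, largely answer the point.

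Most of this stands, and it narrows the point to isolated arm ischemia and to one inconsistent line on death. It does not remove it. Comparability is a reason to report the standard rate as well, not to leave the measured site without an ischemia criterion. A charter should also agree with the protocol table that Section 19.1 cites.

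A reader might infer two stronger things, and the documents support neither:

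- **That such events would vanish from the safety tables.** Sections 10.6 and 19.1 require serious and device-related events to be reported from enrollment, and Section 11.1.2 provides for adverse event and SAE rates. What is at risk is the class or the specific line.
- **That any omission could only favor Sentinel.** Section 11.2.1 foresees crossovers. A Control subject who receives Sentinel stays in Control under ITT, and an event missed there would work the other way.

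**Conclusion.** The point holds in a narrow form and is of low severity. Followed as written, Table 25.2-1 makes isolated new arm ischemia at the Sentinel site at most minor, possibly unclassified, and unadjudicated as a vascular complication. Secondarily, its all-cause death line disagrees with the two lines beneath it and with enrollment and ITT from randomization. The documents do not establish that any death would be lost from mortality; that follows only from a literal reading of the one line.

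The effect is limited to the adjudicated major vascular complication line and, on that literal reading, the all-cause mortality and death-or-stroke lines. Section 11.3.1 says these measurements are not driven by hypotheses. Each event is worth 0.067 percentage points at 1,500 per arm. The primary endpoint, alpha, power and adverse event reporting are untouched. The conclusion assumes that the CEC applies the table as printed; a charter that already provides for arm access would reduce this to an editorial mismatch.

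**What to change.** In Table 25.2-1:

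1. Reword the limb-ischemia criterion as new ipsilateral ischemia of the access limb (the upper extremity for the Sentinel site), documented by symptoms, physical examination and/or decreased or absent flow on imaging of that limb. Also tabulate the major-complication rate under the present wording, so that comparison with trials using standard VARC wording remains possible.
2. Reconcile the death entry by defining all-cause death as death from any cause after randomization.

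Carry both into the CEC charter if it repeats these definitions, and settle the wording before unblinded data are reviewed.

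The cost is a wording change in one table and one extra tabulated rate. No new visit, test or data item is needed, because symptoms or examination suffice and imaging counts only where it was done. The small downside is that a few more events may go to the CEC.
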